### 5.2 Subject disposition

See mock TFLs.

Statistical Analysis Plan  
 Trial ID: NN7088-4595  
 UTN: U1111-1235-5905  
 EudraCT No: 2020-003001-58

**CONFIDENTIAL**

Date:  
 Version:  
 Status:  
 Page:

29 January 2021  
 2.0  
 Final  
 9 of 18

**Novo Nordisk**

### 5.3 Primary endpoint analysis

Endpoint title	Time frame	Unit
Number of bleeding episodes	From start of treatment until visit 7	Count

The primary endpoint will be analysed by a Poisson regression model allowing for over-dispersion (using Pearson's chi-square divided by the degrees of freedom) with the logarithm of duration of actual prophylaxis treatment with N8-GP used as offset. Estimates of the annualised bleeding rate (ABR) will be provided with 95% confidence intervals.

Only the observed bleeding episodes will be counted and the offset will be the duration of actual prophylaxis treatment with N8-GP.

A sensitivity analysis based on negative binomial regression model with the logarithm of duration of actual prophylaxis treatment with N8-GP used as offset will also be performed.

Another sensitivity analysis will be performed imputing the number of bleeding episodes for patients that discontinue treatment. For patients prematurely discontinuing treatment, the number of bleeding episodes counting in the analysis will be imputed up to what they could be expected to have had if they had completed the trial on treatment. If e.g. a patient withdraws after 2 months with 3 bleeding episodes, but the patient should have been in the study for 6 months, then this patient will in the analysis count as having had 9 bleeding episodes in 6 months. This is similar to last observation carried forward (LOCF) and will avoid positive bias occurring from patients with many bleeding episodes withdrawing early. For patients withdrawing within 1 month this method is considered to give too uncertain LOCF values, hence imputation will not be attempted for such patients. Instead only the observed bleeds and the observed duration will be used.

ABRs will be summarised in total, by cause of bleed, and by location of bleed (including ABR in baseline target joints).

Bleeding episodes in relation to surgery will not be included in the analysis.

### 5.4 Secondary endpoints analysis

#### 5.4.1 Secondary efficacy endpoints

Endpoint title	Time frame	Unit
Haemostatic effect of N8-GP when used for treatment of bleeding episodes, assessed on a four-point scale for haemostatic response	From start of treatment until visit 7	Count

Statistical Analysis Plan  
 Trial ID: NN7088-4595  
 UTN: U1111-1235-5905  
 EudraCT No: 2020-003001-58

**CONFIDENTIAL**

Date:  
 Version:  
 Status:  
 Page:

29 January 2021  
 2.0  
 Final  
 10 of 18

**Novo Nordisk**

(excellent, good, moderate and none) by counting excellent and good as success and moderate and none as failure.		
Consumption of N8-GP for treatment of bleeding episodes	From start of treatment until visit 7	IU/kg/bleed
Consumption of N8-GP for prophylaxis	From start of treatment until visit 7	IU/kg/year
FVIII trough activity during prophylaxis	From start of treatment (excluding the first exposure) until visit 7	IU/mL

#### 5.4.1.1 Haemostatic effect of N8-GP

Haemostatic effect of N8-GP when used for treatment of bleeding episodes is assessed as success/failure based on a four-point scale for haemostatic response (excellent, good, moderate and none). Excellent and good counts as success and moderate and none as failures. In addition any bleeding episodes with missing response information will be counted as failures.

Specifically this will be done by a logistic regression. The analysis will be performed by use of Proc Genmod in SAS. Correlation within patients will be taken into account using a Generalized Estimation Equations approach with a working correlation matrix with a compound symmetry structure.

Response as measured by the four point scale will also be summarised and listed.

A sensitivity analysis will be performed similar to the primary analysis but only analysing bleeding episodes with recorded responses (i.e. not counting any bleeding episodes with missing response as failures).

The haemostatic effect will be summarised in total, by cause of bleed and by location of bleed (including haemostatic effect in target joints).

Haemostatic effect for bleeding episodes in relation to surgery will not be included in the analysis.

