### 7.1 Discontinuation of trial treatment

A patient who does not fulfil the eligibility criteria (inclusion/exclusion criteria) must not be included in the trial. Inclusion in violation of any of the eligibility criteria is non-compliant with Good Clinical Practice (GCP) procedures and must be reported to the sponsor without delay. This will be handled as an important protocol deviation, and the independent ethics committee (IEC)/institutional review board (IRB) and regulatory authorities must be notified according to local requirements. If there are no safety concerns for the patient, trial treatment may be continued or resumed at the discretion of the investigator after agreement with the sponsor's global medical expert.

A patient may be discontinued from treatment with N8-GP at the discretion of the investigator due to a safety concern.

The trial product must be discontinued, if any of the following applies for the patient:

1. Simultaneous use of an approved or non-approved investigational medicinal product in another clinical trial.
2. Haemostasis not achievable with N8-GP: The bleed cannot be controlled after 48 hours using adequate doses of N8-GP.
3. FVIII inhibitor ( $\geq 0.6$  and  $\leq 5$  BU) as confirmed by re-testing by Central Laboratory that makes treatment (prophylaxis and/or treatment of bleeding episodes) with N8-GP clinically ineffective. see section [8.6](#)

Protocol Trial ID: NN7088-4595	CONFIDENTIAL	Date: Version: Status: Page:	05 July 2021 4.0 Final 41 of 102	Novo Nordisk
-----------------------------------	---------------------	---------------------------------------	---	---------------------

4. FVIII inhibitor (>5 BU) as confirmed by re-testing by Central Laboratory.
5. Allergy/anaphylaxis to the trial product.
6. Use of Coagulation Factors FVIII, FIX and FVII-containing products other than N8-GP and other FVIII-containing products such as fresh frozen plasma or cryoprecipitate (**Exception:** FVIII is allowed until 96 hours before visit 2a).
7. Incapacity or unwillingness to follow the trial procedures.
8. Use of Anti-coagulants such as Heparin and vitamin-K antagonists (Heparin is allowed for sealing of central venous access devices according to local practice).

See Section [1.2](#) for data to be collected at the time of treatment discontinuation (discontinuation of treatment visit; Visit 7a) and follow-up and for any further evaluations that need to be completed.

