### 8.1.1.2 Definition of Haemostatic Response:

- **Excellent:** abrupt pain relief and/or unequivocal improvement in objective signs of bleeding within approximately 8 hours after a single infusion.
- **Good:** definite pain relief and/or improvement in signs of bleeding within approximately 8 hours after one infusion, but possible requiring more than one infusion for complete resolution
- **Moderate:** probable or slight beneficial effect within approximately 8 hours after the first infusion; usually requiring more than one infusion
- **None:** no improvement, or worsening of symptoms

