## 5 Statistical analyses

### 5.1 General considerations

Novo Nordisk will be responsible for the statistical analyses. The statistical analysis plan (SAP) will be finalised prior to first patient first visit.

Summaries for continuous endpoints will include total number (N), mean (SD), median and min/max, and for pharmacokinetic endpoints also geometric mean and coefficient of variation (CV%). Summaries for categorical endpoints will include N, number (n) and percentages (%) for each outcome category.

In general, all summaries and analyses will also be prepared by age subgroup (12-17 and 18-70 years of age).

FVIII activities below lower limit of quantification (LLOQ) will be set to half the value of the LLOQ.

All bleeding endpoints will be evaluated based on bleeding episodes requiring treatment with N8-GP. Non-treatment requiring bleeding episodes will only be listed. Bleeding episodes in relation to surgery will also only be listed, i.e. not included in the analysis of bleeding endpoints.

Multiple bleeding locations occurring from the same event (e.g. due to a bicycle accident) or at the same time point will be counted as one bleeding episode and only one haemostatic response will be considered for the bleeding episode. In case different responses were registered for different bleeding locations in such a bleeding episode, the worst response will be used in the analysis.

A re-bleed is defined as a worsening of symptoms in the same location after an initial period of improvement, either on treatment or within 72 hours after stopping treatment. If a bleed occurs in the same location later than 72 hours after stopping the treatment it is considered a new bleed. Re-bleeds will only be considered for joint bleeds since the specific location for other bleeds e.g. in subcutaneous are not captured in the database.

In the sub analyses of annualised bleeding rate where there are less than 5 patients in a sub-group, model based estimation will not be done. If no bleedings occur in a sub-group, then the confidence interval will not be calculated.

For patients that discontinue treatment with N8-GP, data after visit P8 will only be included in listings and clearly marked. For secondary safety endpoints separate summary tables for data relating to the period after visit P8 will be prepared if such data is available for 5 or more patients.

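### A bleed rated Good at about 8 hours that later re-bleeds in the same joint, or meets the 48-hour discontinuation criterion, can still be analysed as a haemostatic success, because no rule links these later events to the rating

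*SAP*

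**What the plan says.** **Success rule.** SAP 5.4.1.1 (and Protocol 9.4.3.1) states: "Excellent and good counts as success and moderate and none as failures". The only addition is that "any bleeding episodes with missing response information will be counted as failures". The analysis is a logistic regression with GEE for correlation within patients.

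**Rating scale.** Protocol 8.1.1.2 ties Excellent and Good to the early response. Good requires improvement "within approximately 8 hours after one infusion, but possible requiring more than one infusion for complete resolution". None is "no improvement, or worsening of symptoms", with no time window.

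**Re-bleeds.** SAP 5.1: "A re-bleed is defined as a worsening of symptoms in the same location after an initial period of improvement". The window for this covers the treatment itself and the 72 hours that follow its end. A bleed in the same location after that window is a new bleed. The re-bleed concept is limited to joints, because the exact site of other bleeds is not in the database. No analysis section of the SAP uses the definition.

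**Worst response.** SAP 5.1 takes the worst rating when one episode involves several locations with different ratings. It does not extend this to a later re-bleed.

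**48-hour criterion.** Under discontinuation criterion 2 in Protocol 7.1, trial product must stop if "The bleed cannot be controlled after 48 hours using adequate doses of N8-GP". Neither document links this criterion to the response scale.

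**The concern.** Haemostatic response is the endpoint that addresses the first secondary objective, treatment of bleeds. The trial is single-arm and open-label, so no comparator offsets a misclassified outcome. If 8-hour ratings stand, the success rate can credit N8-GP with a bleed that later worsened, or with one for which the protocol stopped the product because haemostasis was not reached. Any such error is favourable to the product. The re-bleed part falls on joint bleeds, which Protocol 2.2 describes as the commonest manifestation of the disease.

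The rules are also uneven. An unrecorded response is a failure by rule, while a documented 48-hour failure has no rule at all.

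**Working it through.** The documents give no target, margin or power calculation for this endpoint, so there is no figure to reproduce. The check is a reading of the rules, followed by an illustration of scale.

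**Step 1: follow two bleeds through the rules.**

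| Event | Rating available | Success or failure | Counted in the ABR |
|---|---|---|---|
| Joint bleed, improved at 8 h, worsens on treatment or within 72 h of stopping | Good (8-hour improvement) or None (worsening, no time limit) | Not decided; success if the 8-hour rating is kept | Once; by implication the re-bleed is not a new bleed |
| Bleed improved at 8 h, uncontrolled after 48 h | Good remains possible | Success if the 8-hour rating is kept | Once, as an observed bleed |

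In the first row two categories apply to one event and fall on opposite sides of the success line. In the second row nothing in SAP 5.4.1.1 overrides the rating.

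**Step 2: inputs for scale.**
- 36 patients planned (Protocol 1.1); 28 weeks = 196 days of treatment.
- Success rate 88%, programme figure for first treatment assessed within 8 hours (Protocol 2.2).
- ABR 1.18, the programme median for adults and adolescents (Protocol 2.2), used as the low end for the mean. The high end of 3 is an assumption.
- The number of reclassified bleeds, *k*, is unknown; 1 to 3 is shown.

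**Step 3: expected bleeds.** Patient-years = 36 × 196 / 365.25 = 19.3. Bleeds = 19.3 × 1.18 ≈ 23, or 19.3 × 3 ≈ 58.

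**Step 4: success rate = (successes − *k*) / bleeds.**

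| *k* | 23 bleeds, 20 successes | 58 bleeds, 51 successes |
|---|---|---|
| 0 | 87.0% | 87.9% |
| 1 | 82.6% | 86.2% |
| 2 | 78.3% | 84.5% |
| 3 | 73.9% | 82.8% |

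Per bleed: 1/23 = 4.3 points; 1/58 = 1.7 points. For comparison, the exact 95% interval for 20/23 is 66% to 97%, ignoring correlation within patients.

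**Step 5: effect on the ABR if joint re-bleeds were counted as new.** Each adds 1/19.3 ≈ 0.05 per year. One to three re-bleeds would move 1.19 (23/19.3) to 1.24–1.35, or 3.00 to 3.05–3.16.

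**The case against.** The strongest reply is that the plan does not fix these bleeds as successes. None has no time limit, and its wording on worsening matches the SAP's re-bleed definition, so a re-bleed can already be rated a failure. Protocol 8.7 has the site go through the diary ratings with the patient at each visit. Protocol 4.1.4 describes the 48-hour event as a haemostatic response not achieved, which sits more naturally with Moderate or None than with Good. This stands as far as it goes: the result is open, not settled in favour of success. It does not remove the gap. Two sites could rate the same event in opposite ways, no text asks for re-rating after a re-bleed, and Protocol 8.7 lets only the patient or caregiver change the diary entry, apart from severity and treatment type.

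A reader might infer that these failures vanish from both efficacy results. The documents do not support that. A 48-hour failure is still one observed bleed in the ABR. It is also recorded as the reason for discontinuation, and the patient enters the imputation sensitivity analysis unless treatment ended within 1 month. For a joint re-bleed the original bleed is counted; treating worsening inside 72 hours as the same episode is a reasonable way to avoid double counting. Injections and IU/kg per bleed (SAP 5.4.1.2) would show the extra treatment, though they do not correct the success rate.

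A reader might also infer that non-joint re-bleeds are counted as new bleeds. SAP 5.1 says only that re-bleeds are not considered outside joints; how those bleeds are counted is not stated.

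Finally, the 8-hour basis matches the programme's 88%, no hypothesis is tested, and no success threshold is set. A shift of a few points therefore changes no formal decision. That limits the consequence, and it is a good reason to keep the 8-hour summary.

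**Conclusion.** The point holds as a gap in classification. A bleed rated Good at about 8 hours can remain a success after a joint re-bleed or after meeting discontinuation criterion 2, because nothing in SAP 5.4.1.1 or Protocol 9.4.3.1 connects these events to the rating. For a re-bleed, Good and None overlap and no rule chooses between them. It would go too far to say that such bleeds must count as successes.

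The size is about 1.7 to 4.3 percentage points per reclassified bleed, assuming 58 to 23 bleeds from 36 patients treated for 28 weeks at an ABR of 3 to 1.18. The documents give no basis for how many such bleeds to expect, so the total effect cannot be stated. The point should be settled before database lock because the repair is small and the direction of any error is known.

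**What to change.** These changes concern analysis classification only; they leave treatment and discontinuation rules as they are.

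1. In SAP 5.4.1.1 and Protocol 9.4.3.1, count as a failure, whatever its 8-hour rating, any bleed that meets discontinuation criterion 2 or that, after N8-GP has been given for it, is treated with another FVIII product.
2. Add one sensitivity analysis: repeat the planned GEE model with every bleed that has a joint re-bleed as defined in SAP 5.1 also counted as a failure.
3. Keep the 8-hour four-point distribution as a summary, for comparison with the pivotal trial.
4. State in Protocol 8.1.1.2 and the SAP whether the rating is fixed at about 8 hours or covers the whole episode, so that Good and None do not overlap. Do not limit None to 8 hours unless item 2 is in place, since that would remove the only present route by which later worsening becomes a failure.
5. Say outright in SAP 5.1 that a joint re-bleed up to 72 hours after stopping treatment belongs to the original episode in the ABR, if that is the intention.

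**Cost.** Some SAP and protocol wording, one repeat of a planned model, and possibly a slightly less favourable success rate. The discontinuation reason is already collected, and SAP 5.1 implies that joint location is too. The sponsor should confirm that the diary and eCRF data allow a re-bleed to be identified, since no visible text describes a specific flag for it.

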#### 5.4.1.2 Consumption of N8-GP for treatment of bleeding episodes

The number of injections per bleed will be summarised and listed.

The number of IU/Kg per bleed will be summarised and listed.

#### 5.4.1.3 Consumption of N8-GP for prophylaxis

The number of injections for prophylaxis will be summarised and listed.

Statistical Analysis Plan  
 Trial ID: NN7088-4595  
 UTN: U1111-1235-5905  
 EudraCT No: 2020-003001-58

~~CONFIDENTIAL~~

Date:  
 Version:  
 Status:  
 Page:

29 January 2021  
 2.0  
 Final  
 11 of 18

**Novo Nordisk**

The number of IU/Kg per month and per year will be summarised and listed.

#### 5.4.1.4 FVIII trough activity during prophylaxis

The trough and recovery levels will be analysed by a mixed model on the log-transformed plasma concentrations with age group as fixed effect and patient as a random effect. The mean trough and recovery levels will be presented back-transformed to the natural scale together with the 95% confidence interval.

The following rules will be implemented for the analysis of trough and recovery levels:

- Pre-dose and post-dose values will be excluded if post-dose activity is  $\leq$  pre-dose activity.
- Pre-dose and post-dose values taken more than  $\pm 2$  days outside of dosing interval will be excluded.
- Pre-dose and post-dose values taken less than twice the prophylaxis treatment interval after last treatment of a bleeding episode will be excluded.
- Pre-dose and post-dose values taken within 2 weeks after surgery will be excluded.
- Pre-dose and post-dose values taken in relation to the first exposure will be excluded.
- FVIII activity measured in defrosted plasma samples will be excluded.

Furthermore, trough and recovery (30 minutes post-dose) levels measured at scheduled visits will be summarised and listed. Incremental recoveries will be calculated and presented in summary tables and plots.

#### 5.4.2 Secondary safety endpoints

Endpoint title	Time frame	Unit
Incidence rate of confirmed FVIII inhibitors $\geq 0.6$ BU	From start of treatment until visit 7	Rate
Number of adverse events (AEs)	From start of treatment until end of trial	Count
Number of serious adverse events (SAEs)	From start of treatment until end of trial	Count

Statistical Analysis Plan  
 Trial ID: NN7088-4595  
 UTN: U1111-1235-5905  
 EudraCT No: 2020-003001-58

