7. HIV positive, defined by medical records, with CD4+ count  $\leq 200/\mu\text{L}$  and a viral load  $>200$  particles/ $\mu\text{l}$  or  $>400000$  copies/mL within 6 months of the trial entry. If the data are not available in medical records within last 6 months, then the test must be performed at screening visit.
8. Previous significant thromboembolic events (e.g. myocardial infarction, cerebrovascular disease or deep venous thrombosis) as defined by available medical records.
9. Hepatic dysfunction defined as aspartate aminotransferase (AST) and/or alanine aminotransferase (ALT)  $>3$  times the upper limit of normal combined with total bilirubin  $>1.5$  times the upper limit of normal at screening, as defined by central laboratory.
10. Renal impairment defined as estimated glomerular filtration rate (eGFR)  $\leq 30$  mL/min/1.73 m^2 for serum creatinine measured at screening, as defined by central laboratory.
11. Platelet count  $<50 \times 10^9/\text{L}$  at screening based on central laboratory values at screening.
12. Ongoing immune modulating or chemotherapeutic medication.
13. Any disorder, except for conditions associated with haemophilia A, which in the investigator's opinion might jeopardise the patient's safety or compliance with the protocol.
14. Mental incapacity, unwillingness or language barriers precluding adequate understanding or cooperation.

The criteria will be assessed at the investigator's discretion unless otherwise stated.

Patients are screened at visit 1 and baseline assessments are performed at visit 2a which will take place approximately two weeks after visit 1. At visit 2a trial product is administered for the first time to all patients. Some patients will undergo single-dose PK assessments until visit 2b, which is 4 days after visit 2a. From visit 2b the treatment period consists of an additional 4 visits (visits 3-6) taking place 4, 8, 12, and 20 weeks after visit 2a. An end of treatment visit (visit 7) is placed 28 weeks after visit 2a. Patients who underwent single-dose PK assessments at visit 2a will undergo

Protocol  
Trial ID: NN7088-4595~~CONFIDENTIAL~~Date:  
Version:  
Status:  
Page:05 July 2021  
4.0  
Final  
12 of 102**Novo Nordisk**

steady-state PK assessments at visit 7. An end of trial (follow-up) visit (P8) is placed 30 days after the end of treatment visit (visit 7) (visit windows are not included in this description).

Major and minor surgery is allowed in the trial.

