Protocol  
Trial ID: NN7088-4595Date: 05 July 2021 | Status: Final  
Version: 4.0 | Page: 16 of 102 | Novo Nordisk

	Protocol Sections	Screening	Baseline a, b	Treatment period					End of treatment	Discontinuation of treatment	End of trial (Follow up)	Surgery
Visit		V1	V2a	V2b	V3	V4	V5	V6	V7	V7a	P8	
Timing of Visit (Weeks)		-2	0		4 days after visit 2a	4	8	12	20	28	30D	
Visit Window (Days)		-7	0		0	±7	±7	±7	±7		+5	
HIV d	10.2	X										
Factor VIII Inhibitor in Plasma	10.2.8.6.1	X e	X e		X f	X f	X f	X f	X f	X f		
Anti-N8-GP antibodies	8.6.2	X	X		X	X	X	X	X	X	X	
Anti-PEG antibodies	8.6.3		X							X	X	
Anti-HCP antibodies	8.6.4		X							X g		
PK b	1.2.8.5		X e							X		
Administration of Trial Product	4.1.1		X		X	X	X	X	X		X	
Drug Dispensing	6.2		X		X	X	X	X	X		X	
Dispensing Visit	6.2		X		X	X	X	X	X		X	
Drug Accountability	6.2, 6.4		X		X	X	X	X	X		X	

Protocol  
Trial ID: NN7088-4595Date: 05 July 2021 | Status: Final  
Version: 4.0 | Page: 17 of 102

	Protocol Sections	Screening	Baseline a, b	Treatment period					End of treatment	Discontinuation of treatment	End of trial (Follow up)	Surgery
Visit	V1	V2a	V2b	V3	V4	V5	V6	V7	V7a	V7	P8	
Timing of Visit (Weeks)	-2	0		4 days after visit 2a	4	8	12	20	28		30D	
Visit Window (Days)	-7	0	0	±7	±7	±7	±7	±7	±7		+5	
IWRS session	6.2 , 6.3	X	X	X	X	X	X	X	X			
Hand Out and Instruct in Diary	8.7			X	X	X	X	X	X			
Home treatment training	8.8			X								
Training in Devices	8.8			X								

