#### Footnotes

- a All screening assessments must be completed and evaluated by the investigator before the patient can be included in the trial.
- b Refer to [Table -1](#) for patients that will participate in PK assessments
- c To be measured pre-injection and 30 min (± 10min) post-injection.
- d If positive HIV test, then a HIV polymerase chain reaction (PCR) viral load assessment should be performed
- e Time from last treatment with current FVIII product should be at least 96 hours. The blood sample should be taken before any injection of N8-GP, if applicable.
- f Time from last treatment with N8-GP should be at least 96 hours. The blood sample should be taken before any injection of N8-GP, if applicable.
- g Only to be assessed in case of an acute, severe allergic/anaphylactic reaction.
- h Neurological assessments should not be performed for the assessments not performed at baseline (visit 2a).

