## 8.6 Immunogenicity assessments

### 8.6.1 FVIII inhibitors

All patients will be examined for the development of FVIII inhibitors at scheduled visits (see Section [1.2](#)). If FVIII inhibitor development is suspected (e.g., increased number of bleeding episodes, bleeding episodes difficult to treat, N8-GP recovery and trough levels below expected values) during the course of the trial, additional inhibitor tests can be taken. All inhibitor tests must be analysed by the central laboratory.

A positive inhibitor test is defined as  $\geq 0.6$  BU. In the event that a previously inhibitor negative patient has a positive inhibitor test ( $\geq 0.6$  BU), the patient will be requested to visit the site for additional sampling preferably within 2 weeks. In addition, the following tests should be performed: anti-N8-GP antibodies, anti-PEG antibodies, FVIII trough (pre-dose), FVIII recovery (30 min post-dose) and lupus anticoagulant. These samples should preferably be taken prior to any change of treatment, and after approximately 96 hours wash-out period. If the second (confirmatory) inhibitor test is also positive, the patient must be discontinued from trial treatment if FVIII inhibitor  $>5$  BU or if FVIII inhibitor  $\geq 0.6$  and  $\leq 5$  BU that makes treatment (prophylaxis or treatment of bleeding episodes) with N8-GP clinically ineffective, by discontinuing trial product and attending the discontinuation of treatment visit (visit 7a) within 1 week after the result is available.

If the second (confirmatory) inhibitor test is positive and  $\leq 5$  BU and the investigator judges that the inhibitor does not clinically interfere with N8-GP treatment (prophylaxis or treatment of bleeding episodes), the patient can stay in the trial and continue treatment as per-protocol treatment.

A patient has inhibitor ( $\geq 0.6$  BU) if the patient has been tested positive for inhibitors at two consecutive test samples performed at the central laboratory preferably with no more than 2 weeks between the tests.

For patients discontinued from treatment with N8-GP: A follow-up visit must be scheduled 30(+5) days after the discontinuation of treatment (Visit 7a) and additional follow-up contact(s) (e.g., phone calls) may be arranged as long as clinically warranted up to 3 months after the EOT Visit.

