For patients continuing in the trial with inhibitor ( $\geq 0.6$  and  $\leq 5$  BU): the patient must follow per-protocol treatment schedule and the scheduled visits as described in Section [1.2](#). Additional visits can be scheduled if closer monitoring is needed. Closer monitoring is highly recommended but this decision will be at investigator's discretion. In the event of a concern about reduced treatment efficacy a PK session may be performed. Blood sampling during the PK profile session can be performed at the following time points: pre-dose, 30 minutes ( $\pm 10$  min), 24h ( $\pm 8$  hours), 48h ( $\pm 8$  hours), 72h ( $\pm 8$  hours) and 96h ( $\pm 8$  hours).

A confirmed positive inhibitor is considered to have disappeared if the inhibitor titre is  $<0.6$  BU on 2 consecutive inhibitor tests (performed at 2 consecutive visits) and the FVIII recovery is  $\geq66\%$  of expected values. A patient with repeated positive inhibitor test result will count only once in the determination of the inhibitor incidence rate.

Patients who develop an inhibitor should be classified as high responders (peak inhibitor titre  $>5$  BU), low responders (peak inhibitor titre  $\leq5$  BU), and whether the inhibitor is transient (disappearing (inhibitor titre  $<0.6$  BU on  $\geq2$  consecutive measurements) spontaneously within 6 months without a change in treatment regimen), or not.

All per protocol inhibitor laboratory samples are to be analysed in the central laboratory, and only these results will be used in the data analyses.

Any single positive inhibitor test must be reported as an AESI (see Section [10.3.3](#)).

If the second (confirmatory) inhibitor test is positive then the event must be reported as an SAE (see Section [10.3.5](#)).

Blood samples for measurement of inhibitors towards FVIII will be analysed according to the Nijmegen modification of the Bethesda assay. Any sampling for the inhibitor test must be performed at least 96 hours after last administration of N8-GP to allow for maximum wash-out of the drug.

The patient may discontinue the trial including an EOT Visit and FU Visits or remain in the trial as described above. A patient having an initial positive inhibitor test and a second negative inhibitor test will be regarded as inhibitor negative and can continue in the trial.

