**Novo Nordisk**

#### 5.4.2.1 Incidence Rate of Confirmed FVIII-inhibitors $\geq 0.6$ BU

A patient is said to have FVIII-inhibitors if two consecutive tests, preferably within 2 weeks, are positive ( $\geq 0.6$  BU). The rate of inhibitors will be reported and a 1-sided 97.5% upper confidence limit will be provided based on an exact calculation for a binomial distribution. For the calculation of the inhibitor rate the numerator will include all patients with neutralising antibodies while the denominator will include all patients with a minimum of 50 exposures plus any patients with less than 50 exposures but with neutralising inhibitors.

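### Does an inhibitor first found at visit 7 and confirmed afterwards drop out of the inhibitor rate?

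*SAP*

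**What the plan says.** SAP 5.4.2 names the endpoint "Incidence rate of confirmed FVIII inhibitors" (at least 0.6 BU) and gives its time frame as "From start of treatment until visit 7". In the same table, the AE and SAE counts run to the end of the trial. Protocol 3.2.2.2 and 9.4.3.2 use the same windows.

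SAP 5.4.2.1 defines a case: "A patient is said to have FVIII-inhibitors if two consecutive tests, preferably within 2 weeks, are positive". The numerator is all patients with neutralising antibodies. The denominator is those with at least 50 exposures plus any inhibitor patient with fewer. The result is reported with an exact one-sided 97.5% upper limit.

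The row "Factor VIII Inhibitor in Plasma" in the Protocol 1.2 flowchart has a sample at visit 7, and on timing the synopsis says "An end of treatment visit (visit 7) is placed 28 weeks after visit 2a". The flowchart footnote adds: "The blood sample should be taken before any injection of N8-GP, if applicable".

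Protocol 8.6.1 covers what follows a new positive result: "the patient will be requested to visit the site for additional sampling preferably within 2 weeks". It then says: "If the second (confirmatory) inhibitor test is positive then the event must be reported as an SAE".

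**The concern.** A case needs two samples, but the window has one end date, and neither document says which sample the date governs. For visits 3 to 6 this hardly matters, since a retest within about two weeks still falls before visit 7. At visit 7 it does matter, because the retest must come later.

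A strict reading is conceivable. The endpoint speaks of confirmed inhibitors up to visit 7, and the neighbouring safety endpoints are explicitly given a longer window. A programmer might take that difference as intended and cut inhibitor data at visit 7.

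Visit 7 also carries more weight than one sample in five suggests. For a patient who completes treatment it is the only scheduled inhibitor test after week 20, and it is the one nearest the 50-exposure threshold in the denominator. Under the strict reading, the report could show a rate of 0% beside a confirmed inhibitor in the SAE listing.

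**Working it through.** The plan states no inhibitor rate or sample-size calculation to reproduce. The check has three parts: what visit 7 covers, what one case does to the reported statistic, and which reading the text supports.

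**1. What visit 7 covers.** Visit weeks are from the Protocol synopsis. Assume doses on days 0, 4, 8 and so on, nominal visit days, no bleed doses and no switch to twice-weekly dosing. Exposures before the pre-dose sample are then day/4.

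| Visit | Week | Day | Exposures before sample |
|---|---|---|---|
| 3 | 4 | 28 | 7 |
| 4 | 8 | 56 | 14 |
| 5 | 12 | 84 | 21 |
| 6 | 20 | 140 | 35 |
| 7 | 28 | 196 | 49 |

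The interval seen only by the visit 7 test is (28 − 20)/28 = 29% of the treatment period, or (49 − 35)/49 = 29% of the exposures. Visit 7a, for patients who stop early, also has an inhibitor sample, and Protocol 8.6.1 allows extra tests on suspicion, so 29% is an upper figure.

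**2. Effect of one case.** The statistic is the SAP's exact one-sided 97.5% upper limit. With no cases it is 1 − 0.025^(1/n). With one case it is the p that solves (1 − p)^n + n·p·(1 − p)^(n−1) = 0.025. The value 30 is the planned number of completers, and 36 is the planned enrolment (assuming that all reach 50 exposures). Suppose one patient is first positive at visit 7 and there are no other cases.

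| Situation | Not counted | Counted | Change in upper limit |
|---|---|---|---|
| 30 in denominator | 0/30 = 0%, limit 11.57% | 1/30 = 3.33%, limit 17.22% | 5.65 points |
| 36 in denominator | 0/36 = 0%, limit 9.74% | 1/36 = 2.78%, limit 14.53% | 4.79 points |
| Patient has fewer than 50 exposures, so counting him also adds him to the denominator | 0/29 = 0%, limit 11.94% | 1/30 = 3.33%, limit 17.22% | 5.28 points |

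**3. Which reading the text supports.**

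- The SAP 5.4.2.1 numerator has no date limit on the second sample, and the two-week interval is only a preference.
- Protocol 8.6.1 requests the retest after any new positive in a previously negative patient and makes no exception for the last treatment visit.
- A time frame in an endpoint table ordinarily describes the period of observation. Here, confirmed describes the status of the case.
- For a completer positive at visit 7 (day 196), a retest within the preferred two weeks falls by day 196 + 14 = 210. The follow-up visit P8 is on day 196 + 30 = 226 to 196 + 35 = 231, so the retest precedes it by 16 to 21 days and the patient is still in the trial.
- SAP 5.1 restricts data after P8 to listings or separate tables, but only for patients who discontinue N8-GP. A retest by day 210 would precede P8 in any event.

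All five points lead to counting the patient.

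**The case for a change.** The strongest case for a change is that the rule is nowhere written down, the trial is open-label, and with about 30 patients a single case moves the upper limit by about 5 to 6 percentage points. A choice made after a late positive has been seen could be challenged, and one sentence would prevent that.

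It is true that the sentence is missing and that the arithmetic is as shown. It does not follow that the choice is open. Counting the patient is what the numerator definition prescribes. Leaving him out would require a deadline that the SAP does not contain, so exclusion would be the departure needing defence. The conflict with the SAE listing arises only under that unsupported reading, and it would be visible in the report.

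A fuller rule could also do harm. Suppose a last date for confirmation were set at 35 days after the first positive, which matches the latest P8 for a completer positive at visit 7. Visits 5 and 6 are at weeks 12 and 20, so 8 × 7 = 56 days apart. A patient positive at both, with no retest between them, has two consecutive positive tests and counts under SAP 5.4.2.1 today. A 35-day limit would remove him. Extending the window to visits after visit 7a could bring in inhibitors first detected on another FVIII product, which is debatable for a rate describing N8-GP.

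Two neighbouring wording points hardly affect the rate. Protocol 7.1 dates P8 from the last dose, while 8.6.1 dates it from visit 7a; the sponsor can reconcile these separately. Protocol 7.1 also excludes FVIII activity after visit 7a, while 8.6.1 asks for trough and recovery at the retest. These conflict only if the retest follows visit 7a. In the usual order of 8.6.1 the retest comes first.

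**Conclusion.** The concern does not call for a change. The documents leave unsaid which of the two samples the visit 7 limit governs, but the definition of the numerator and the retest procedure together give one answer: a patient first positive at visit 7 and confirmed afterwards is a case. If he were nevertheless left out, the cost would be one case in a descriptive secondary endpoint, for example 0/30 with an upper limit of 11.6% in place of 1/30 with 17.2%. No hypothesis is tested, and the confirmed inhibitor would still be counted and listed as an SAE. Such cases should be few, since the protocol itself describes the inhibitor risk as low in previously treated patients without an inhibitor history.

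This conclusion assumes that the retest is actually taken when requested and that analysts apply the numerator as worded. The exposure counts further assume nominal dosing every 4 days. A sentence dating each case by its first positive sample would be harmless, but it would only restate what the plan already does.
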